2.2.3. Exploratory Endpoints

The exploratory endpoints for the study are the following:

- Time to second VOC that required admission to a healthcare facility and treatment with parenteral pain medication within 90 days of randomization.
- Rate of complicated VOCs (i.e., acute chest syndrome, hepatic sequestration, splenic sequestration, and priapism) during the 90 days following randomization.
- Rate of inpatient hospital admissions for any reason during the 90 days following randomization.
- Number of days of inpatient hospitalization for any reason during the 90 days following randomization.
- Proportion of participants rated as "very much improved" or "much improved" based on the Patient's Global Impression of Change (PGI-C) at Day 46 and Day 91.
- Proportion of participants rated as "very much improved" or "much improved" based on the Clinician's Global Impression of Change (CGI-C) at Day 46 and Day 91.
- Change from Baseline in the cumulative score for the Adult Sickle Cell Quality of Life Measurement (ASCQ-Me) Pain Impact Short Form over time to Day 91.

2.2.4. Safety Endpoints

The safety endpoints for the study are the following:

- Incidence of treatment-emergent adverse events (TEAEs).
- Change from Baseline in laboratory assessments (complete blood count, chemistry, and coagulation).

2.2.5. Exploratory Pharmacology Endpoints

The exploratory pharmacology endpoints of the study are the following:

- Plasma PK of inclacumab as assessed by population PK analysis using nonlinear mixedeffects modeling.
- Incidence of anti-drug antibodies (ADA) to inclacumab.

Relationships between PK, PD, biomarkers, clinical labs, safety, and efficacy will be explored.

2.3. Determination of Sample Size

The original sample size determination was based on statistical power considerations for the primary efficacy endpoint, the proportion of participants with at least 1 VOC that required admission to a healthcare facility and treatment with parenteral pain medication within 90 days of randomization.

As originally planned, the study was to use a group sequential design to evaluate the primary efficacy endpoint based on 2 sequential analyses: (i) one interim analysis after approximately 75 participants per arm have completed the study through 90 days, and (ii) if required, a final study analysis based on approximately 140 participants per arm.

For the primary endpoint, the planned sample size of up to 280 participants (140 participants per treatment group) was to provide approximately 90% power to detect a targeted 50% relative reduction in the proportion of participants with at least 1 VOC that required admission to a healthcare facility and treatment with parenteral pain control within 90 days, from a rate of 35% for placebo to 17.5% for inclacumab, using a 2-sided test of the difference in 2 binomial proportions (Normal approximation). To maintain an overall Type I error rate of 0.05, calculations assumed an O'Brien-Fleming boundary of the Lan-DeMets alpha-spending function (East® version 6.5). For the sample size calculation, a 5% drop-out rate during the 90-day study period was used.

With this original sample size, the smallest observed treatment difference expected to be statistically significant at the final analysis was approximately a 32% relative reduction (i.e., reduction in the proportion of participants with at least 1 VOC that required admission to a healthcare facility and treatment with parenteral pain medication within 90 days from 35% for placebo to 23.8% for inclacumab).

As of June 2023, the Sponsor has decided to discontinue the study prior to full enrollment, with approximately 26% of the total number of planned participants randomized. The ultimate study sample size is based on screening and enrollment at the time of the decision to discontinue, rather than any statistical considerations.

2.3.1. Basis for Original Sample Size Assumptions

Based on 2016 nationwide re-admission data, a 30-day all cause re-admission rate of 26.9% was reported among patients admitted with a principal diagnosis of sickle cell crisis (Kumar, 2020). The majority (86%) of such re-admissions were due to sickle cell crisis or related diagnosis. Similarly, an analysis of patient claims data (Source Healthcare Analytics Patient Transaction Dataset; August 2017 to July 2018 cohort) showed that among patients with a history of VOC, approximately 50% of patients hospitalized for an index VOC are expected to be re-hospitalized for a VOC within 90 days (data on file). However, overall hospital admissions have decreased with the COVID-19 pandemic (Birkmeyer, 2020) and patients with SCD may try to avoid hospitalizations (McFarling, 2020; Powell, 2020).

In this study, the primary endpoint evaluates, following an index VOC, the occurrence of at least 1 VOC that required admission to a healthcare facility (hospital admission; admission to an emergency room, observation unit, or infusion center for ≥ 12 hours; or 2 visits to an emergency room, observation unit, or infusion center over a 72-hour period) and treatment with parenteral pain medication within 90 days of randomization. For purposes of sample size calculation, it was assumed that approximately 35% of participants in the placebo group experience such a protocol-defined VOC within 90 days of randomization.

The assumption of 5% drop-out rate during the 90-day study period was based on data from the Phase 3 clinical trial of voxelotor, Study GBT440-031, in patients with SCD (data on file).

2.4. Randomization

Eligible participants will be randomized on Day 1 through a central interactive response technology (IRT) system. Randomization may occur up to 5 days following investigator-assessed resolution of index VOC (for example, hospital discharge, completion of parenteral analgesia, or transition to oral analgesics).

Participants will be randomized with a 1:1 ratio to receive treatment with inclacumab or placebo. A stratified permuted block design will be used, with randomization stratified by baseline hydroxyurea (HU) use (yes; no), number of VOCs in the preceding 12 months (2 to 4 episodes; 5 to 10 episodes), and geographic region (North America; rest of world).

On the day of randomization (Day 1), participants will receive a single dose of study drug.

2.5. Analysis Timing

Due to the early termination of the study, the protocol-specified interim efficacy analysis will not occur.

Final study data will be used for all the analyses to be performed for the CSR after all randomized participants have completed the study or discontinued early (i.e., last participant's last visit has occurred), and all corresponding data have been entered into the database, reviewed, and verified and the database is locked.

3. GENERAL CONSIDERATIONS

3.1. Definitions and Terminology

Study Drug

The term study drug refers to either inclacumab or placebo.

Baseline Value

Baseline is defined as the last available pre-treatment value taken on or before the day of randomization, and will be used for summary of baseline characteristics and change-from-baseline analyses, as appropriate. For ASCQ-Me, baseline is defined as the assessment taken on the day of randomization.

Day 1

Day 1 is the date of randomization.

Study Day

Study Day is defined relative to the date of randomization.

For study assessments or events that occur on or after the date of randomization, study day is calculated as:

Study Day = Event Date - Randomization Date + 1.

For study assessments or events that occur before the date of randomization, study day is calculated as:

Study Day = Event Date – Randomization Date.

Study Visit

Study Visit is the protocol visit as shown in Table 1.

Treatment Day

Treatment Day is defined relative to the date of first dose of study drug.

For study assessments or events that occur on or after the date of first dose, treatment day is calculated as:

Treatment Day = Event Date - First Dose Date + 1.

For study assessments or events that occur before the date of first dose, treatment day is calculated as:

Treatment Day = Event Date – First Dose Date.

Treatment-Emergent Adverse Event

Treatment-emergent adverse events (TEAEs) are defined as adverse events that occur on or after Day 1 of study treatment or the worsening of a preexisting condition on or after Day 1 of study treatment. Note: Given the long half-life of inclacumab, events occurring through end of study will be considered treatment emergent.

Study Completion

Completion of study is specified on the End of Study (EOS) CRF. Participants are considered to have completed the study if (1) the subject completed the study through the Day 91 visit and elected to enroll in the open-label extension study, or (2) the subject did not enroll in the open-label extension study and completed the study through the Day 161 visit.

Treatment Completion

Completion of treatment is specified on the End of Treatment (EOT) CRF and includes all participants who did not permanently discontinue study drug early.

3.2. Visit Windows

For summaries by timepoint (e.g., CGI-C, PGI-C, vital signs, laboratory values), analysis visit windows will be used to classify assessments based on the actual study day of the measurement regardless of the original nominal visit label. This includes assessments collected at Unscheduled, Early Termination, or EOS visits. Target study days, the protocol-specified study day windows, and the analysis visit windows are shown in Table 1.

Table 1: Analysis Windows for Assessments Other than ASCQ-Me

Study Visit	Target Study Day	Visit Window per Protocol (study days)	Window for Statistical Analysis (study days)
Screening	-	[-10, -1]	[-10, -1]
Day 1	1	1	1
Day 46	46	[39, 53]	[32, 60]
Day 91	91	[84, 98]	[77, 105]
Day 161	161	[147, 175]	[140, 182]

ASCQ-Me=Adult Sickle Cell Quality of Life Measurement,

Note: Baseline is defined as the last available pre-treatment value taken on or before the day of randomization. Note: If multiple measurements fall within the statistical analysis window, the measurement closest to the target study day will be used. If two measurements are equally close, the earlier value will be used.

For the ASCQ-Me questionnaire (completed weekly at home), the analysis windows shown in Table 2 will apply for data summary.

Table 2: Analysis Windows for Assessment of ASCQ-Me

Analysis Timepoint	Target Study Day	Window for Statistical Analysis (study days)
Baseline	1	1
Week 1	8	[2, 11]
Week 2	15	[12, 18]
Week 3	22	[19, 25]
Week 4	29	[26, 32]
Week 5	36	[33, 39]
Week 6	43	[40, 46]
Week 7	50	[47, 53]
Week 8	57	[54, 60]
Week 9	64	[61, 67]
Week 10	71	[68, 74]
Week 11	78	[75, 81]
Week 12	85	[82, 88]
Week 13	92	[89, 95]

ASCQ-Me=Adult Sickle Cell Quality of Life Measurement

Note: Baseline is defined as the assessment taken on the day of randomization. If multiple measurements fall within the statistical analysis window, the measurement closest to the target study day will be used. If two measurements are equally close, the earlier value will be used.

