5.3.3. Vital Signs

Measurements of heart rate (HR), blood pressure (BP), and body temperature will be obtained. Additional vital signs may be taken at any other time, if deemed necessary.

HR and BP measurements will be performed with participants in a supine position for at least 5 minutes, except when they are seated or semi-reclined because of study procedures and/or AEs (eg, nausea, dizziness) or if deemed necessary by the Investigator or designee.

At the Baseline Visit (Day 1) vital signs will be collected prior to the Baseline blood collection and prior to study drug administration. Vital signs will also be collected at the completion of infusion and at one hour after completion of infusion. Participants should be clinically well with stable vital signs and without signs or symptoms of an infusion-related reaction prior to release from observation.

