5.4.4. Vital Signs and Weight

[figure not shown]
Descriptive summaries of vital signs (e.g., systolic and diastolic blood pressure, heart rate, and body temperature) at baseline and each evaluation post baseline, as well as changes from baseline over time, will be generated by treatment group. In addition, descriptive summaries of weight at baseline will be generated by treatment group.

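### SAP 3.2 and SAP 5.4.4 conflict on Day 1 vital signs: taken literally, the window rule drops both post-infusion readings from the by-arm summaries

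*SAP*

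**What the plan says.** **What is collected.** Protocol 5.3.3 (Vital Signs) sets the first reading: "At the Baseline Visit (Day 1) vital signs will be collected prior to the Baseline blood collection and prior to study drug administration". It then adds two more: "Vital signs will also be collected at the completion of infusion and at one hour after completion of infusion". The vital-signs footnote to Protocol Appendix 1 repeats this schedule.

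**How values are selected.** SAP 3.2 (Visit Windows) names vital signs among the by-timepoint summaries that use analysis windows. The windows "will be used to classify assessments based on the actual study day of the measurement regardless of the original nominal visit label". Table 1 has one Day 1 row, with target day 1 and window day 1. Its note reduces each window to one value: "If multiple measurements fall within the statistical analysis window, the measurement closest to the target study day will be used". It continues: "If two measurements are equally close, the earlier value will be used". SAP 3.1 counts time in calendar days: "Study Day = Event Date - Randomization Date + 1".

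**What is promised.** SAP 5.4.4 (Vital Signs and Weight) says that vital signs will be summarised by treatment group "at baseline and each evaluation post baseline, as well as changes from baseline over time". SAP 3.1 defines baseline as the last value before treatment, so the two post-infusion readings are post-baseline evaluations.

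**The concern.** The selection rule in 3.2 and the commitment in 5.4.4 give different tables. A programmer who follows 3.2 produces a Day 1 row holding the pre-dose value, and the next row is Day 46. A programmer who follows 5.4.4 produces end-of-infusion and one-hour rows as well.

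The difference falls on the only infusion in the trial. Safety is part of the primary objective, SAP 5.4 lists vital signs among its three descriptive safety assessments, and the infusion-related reaction is the SAP's only adverse event of special interest. Protocol 7.3 lists hypotension among the signs of such a reaction. If 3.2 is followed, the vital-sign tables could appear to show no effect of the infusion when the readings closest to it were never in them.

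**Working it through.** The plan states no figure on this point, so there is none to reproduce. The check applies the selection rule to the scheduled readings.

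**Inputs**
- Day 1 readings: pre-dose, end of infusion, one hour after (Protocol 5.3.3).
- Dosing takes place on the day of randomization (SAP 2.4; Protocol 4.8.2).
- Study day in whole days (SAP 3.1); Day 1 target 1, window 1 (SAP 3.2, Table 1).
- About 26% of 280 planned participants randomized (SAP 2.1 and 2.3).

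**Step 1: study day.** For a reading taken on the randomization date, study day = 0 + 1 = 1. This holds for all three readings.

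**Step 2: distance to target.** Distance = |study day − target day|.

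| Reading | Study day | Distance | Order in time |
|---|---|---|---|
| Pre-dose | 1 | \|1 − 1\| = 0 | first |
| End of infusion | 1 | 0 | second |
| One hour after | 1 | 0 | third |

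**Step 3: tie rule.** All three tie, and the earlier value wins. The pre-dose reading is kept and 2 of 3 sets are dropped. The note speaks of two tied measurements; applying it to three is an extension, but the SAP gives no other rule.

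**Step 4: consequence for Day 1.** The kept value is normally the baseline itself, so the Day 1 change from baseline is baseline − baseline = 0 by construction.

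**Step 5: next available row.** Table 1 has no window between Day 1 and the Day 46 analysis window, which runs from Day 32 to Day 60. If an infusion ran past midnight, a Study Day 2 reading would fall in no window and also be left out.

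**Step 6: scheduled post-dose timepoints in the summaries.** As collected there are five: end of infusion, one hour, Day 46, Day 91 and Day 161. Under the literal rule there are 5 − 2 = 3. Day 161 applies only to participants who do not enter the extension study; for those who do, the count goes from 4 to 2.

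**Step 7: volume.** 280 × 0.26 = 72.8, about 73 participants. 73 × 2 = 146 post-infusion sets. This is an upper figure: it assumes that every randomized participant was dosed and had both readings taken.

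**The case against.** The strongest reply is that the loss is not established. SAP 5.4.4 is the section specific to vital signs, and on its face it covers both post-infusion readings. The rule in 3.2 sets aside the nominal visit label and refers to unscheduled, early-termination and end-of-study visits. That suggests its purpose is to reassign off-schedule visits and remove duplicates, not to collapse planned readings within one visit. A Day 1 change that is zero by construction is also unlikely to have been intended. The table mock-ups sit in a separate document (SAP 6) and may already have the extra rows.

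Much of this stands, and it is why the point is a conflict and not a proven loss. It does not remove the conflict. Section 3.2 names vital signs and gives an operational rule; 5.4.4 defines no within-day timepoints and does not exempt itself from 3.2. The precedence statement in SAP 2 ranks the SAP over the protocol, not one SAP section over another.

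A reader might go further and infer that the safety objective loses its only data on acute exposure. The documents do not support that:
- Every infusion-related reaction is recorded as an event of special interest or a serious adverse event (Protocol 4.6) and summarised by arm (SAP 5.4.2).
- Adverse events count as treatment-emergent from Day 1 (SAP 3.1). Those leading to study drug interruption or discontinuation have their own summaries (SAP 5.4.2).
- Infusion interruptions are summarised by arm (SAP 5.4.1).
- Clinically significant vital-sign changes are recorded as adverse events (opening of the Protocol's Assessment of Safety section).

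The listed safety endpoints are treatment-emergent adverse events and laboratory change (SAP 2.2.4), so vital signs are not among them.

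**Conclusion.** SAP 3.2 and 5.4.4 are inconsistent on Day 1 vital signs. If 3.2 is applied literally, the selection rule defeats the summary that 5.4.4 promises: 2 of 3 Day 1 sets leave the by-arm tables, up to about 146 sets in all. These are the only scheduled vital-sign readings between dosing and the Day 46 visit. The readings are still collected; only their place in the summaries is in doubt.

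What is at risk is the descriptive change from pre-dose in blood pressure, heart rate and temperature, by arm. The remaining sources of acute safety data are event-based or depend on the investigator's judgement, so they would not show a shift in the mean or distribution that was not judged clinically significant.

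The conclusion rests on same-day dosing and on the literal reading of 3.2. The volume also assumes about 73 participants dosed and fully measured. No endpoint, test or decision rule depends on these summaries, so the severity is minor.

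**What to change.** - **SAP 3.2 and Table 1:** classify Day 1 vital signs by nominal within-day timepoint (pre-dose, end of infusion, one hour after the end of infusion) and exempt them from the one-value-per-window rule, including its tie-break.
- **SAP 5.4.4:** state that change from the pre-dose reading is summarised by treatment group at both post-infusion timepoints.
- **Mock-ups:** confirm that the vital-sign table has these two rows.

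The cost is a few lines of SAP wording and two rows in an existing table. Protocol 5.3.3 already requires the readings, so no new data are needed.

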4. ANALYSIS POPULATIONS

Two main analysis populations are defined for this study: the intent-to-treat (ITT) population and the safety population.

4.1. Intent-to-Treat Population

The ITT population includes all randomized participants. For analyses based on this population, participants will be grouped according to treatment assigned at randomization.

The ITT population will be the main analysis population for efficacy analyses and summaries of demographic and baseline characteristics.

4.2. Safety Population

The safety population includes randomized participants who received treatment with study drug. For analyses based on this population, participants will be grouped according to the actual study treatment received. Any participant who receives treatment with inclacumab will be classified in the inclacumab treatment arm. Participants who receive treatment with placebo only will be classified in the placebo treatment arm.

The safety population will be the primary analysis population for safety and exposure data.

5. STATISTICAL METHODS

5.1. Summaries of Study Conduct

The number of participants randomized will be tabulated by region, country, study site, and treatment group. Participant disposition (the number of participants randomized, treated, and completing the study) will be tabulated by treatment group. Reasons for study drug interruption and discontinuation, as well as study discontinuation, will be summarized.

Any eligibility criteria deviations, dosing errors, and other significant protocol deviations will also be tabulated by treatment group and evaluated for potential impact on the interpretation of study results.

5.2. Summaries of Demographic, Baseline Characteristics, and Concomitant Medications

Demographic and baseline characteristics (such as age, sex, race, body weight in kg, estimated glomerular filtration rate [eGFR], sickle cell genotype, number of VOCs in the 12 months prior to the screening visit, baseline HU use, baseline voxelotor use, prior crizanlizumab use, and geographic region) will be summarized for the ITT population by treatment group.

Medical history will be coded using Medical Dictionary for Regulatory Activities (MedDRA; the most current version at the time of the analysis will be used) and summarized for each treatment group. Prior and concomitant medications will be coded using the World Health Organization (WHO) Drug Dictionary and summarized.

Time on study, defined as time from randomization (Day 1) to the participant's end of study date, will also be tabulated.

5.3. Efficacy Analyses

Efficacy analyses will be based on the ITT patient population (Section 4.1), with participants grouped according to the treatment assigned at randomization. Data from all randomized participants, regardless of treatment with study drug or adherence to the protocol will be included in the efficacy analyses.

Covariate Adjustment

Unless otherwise noted, analyses of primary and secondary efficacy endpoints will be adjusted for the following randomization stratification variables:

- Baseline HU use (yes; no)
- Number of VOCs in the 12 months prior to study entry (2 to 4 episodes; 5 to 10 episodes)

If convergence or model issues arise, then analyses will be simplified by excluding one of the above stratification variables.

Note: The additional randomization stratification variable of geographic region (North America; rest of world) will not be included in the analyses due to the early study discontinuation and the low number of subjects enrolled from North America.

For stratification variables, the value recorded in the clinical database (i.e., per case report form) will be compared to value captured in the IRT. If differences are observed, the values from the clinical database will be used in the analysis.

Statistical Tests

No adjustment for multiple comparisons will be performed.

